### **6.5.1 Permanent Suspension of Study Treatment**

Permanent suspension of study treatment must occur in the following cases:

- If, in the view of the investigator, the patient experiences a severe allergic reaction that cannot be explained by the administration of any other medication.
- Development of liver function abnormality, as described in Section 9.2.11.3.
- Development of an AE or any medical condition, which, in the opinion of the investigator, necessitates permanent suspension of study treatment.
- If the patient did not tolerate the starting dose of 5 mg/kg of body weight b.i.d.
- Withdrawal of consent.

Patients have the right to discontinue study treatment for any reason. However, unless they withdraw consent and are no longer willing to participate, they should be followed for the remainder of the trial and all AEs should be reported, regardless of whether or not the event occurs under the care of another physician or institution.

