### **6.5.3 Withdrawal of Consent**

Patients may decide to fully or partially withdraw their consent to participate in the study. At that point, it should be established, whether the withdrawal is related to study treatment, further assessments, or any further involvement in the study. If the withdrawal is primarily related to study treatment or specific assessments, patients should be encouraged to continue follow-up and to attend all other subsequent study assessments. Reports of AEs and SAEs should be collected until completion of the study for all withdrawals, unless the patient objects to such follow-up.

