#### ***Start of study medication in the evening of Day 1.***

#### Visit 2 (Day 3 + 2 days) – This visit may be performed as a virtual visit if an in-person visit is not possible as long as the ECG recording can be obtained

The following evaluations will be performed on Day 3 after start of study medication:

- Vital signs, including HR and blood pressure (if visit in person)
- Review/collection of daily diary NRS pain scores, if not submitted electronically to Patient Portal if the patient has completed the questionnaire on paper

- 12-lead ECG 5 hours post morning dose (time window 3.5 – 6 hours); QTc intervals on ECG to be reviewed by site investigator, or designate, who decides if patient can continue study medication. If the visit is done remotely, the patient will record the ECG on a portable device at home or will have the ECG recording performed at a local clinic. The tracings must immediately be transmitted to the site for review.
- Study drug dose increase to 7.5 mg/kg of body weight b.i.d. if patient tolerating starting dose of 5 mg/kg of body weight b.i.d. (If patient did not tolerate the starting dose of 5 mg/kg of body weight b.i.d., the patient will stop the study medication but will continue in the study and follow all assessments until Visit 5 to be included in the safety analyses)
- Study drug accountability
- Recording of changes in concomitant medications
- AE and SAE recording

Visit 3 (Day 10 ± 2 days) – This visit may be performed as a virtual visit if an in-person visit is not possible as long as the ECG recording can be obtained

The following evaluations will be performed on Day 10 after start of study medication:

- Vital signs, including HR and blood pressure (if visit in person)
- Review/collection of daily diary NRS pain scores, if not submitted electronically to Patient Portal if the patient has completed the questionnaire on paper
- Collect highest NRS pain score within the past 7 days
- 12-lead ECG 5 hours post morning dose (time window 3.5 – 6 hours); QTc intervals on ECG to be reviewed by site investigator, or designate, who decides if patient can continue study medication. If the visit is done remotely, the patient will record the ECG on a portable device at home or will have the ECG recording performed at a local clinic. The tracings must immediately be transmitted to the site for review.

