**4 Study drug adjustment up to Visit 4 (Week 3); drug accountability at all visits, including virtual visits**

 Adverse Event recording starts after informed consent is obtained

 All local laboratory assessments at baseline to be performed before start of study Rx

 Pregnancy test in women with childbearing potential

 For patients not able to participate in the EP, Visit 5 (Week 8) is the end of study visit  
 EP starting after Visit 5 until Visit 9

 If CRP was measured within 3 days

If CRP was measured within 7 days of Day 1, this value will be used as the baseline value. If there is no CRP measurement available within 7 days of Day 1, CRP needs to be measured at baseline.

Highest NRS pain score within the past 7 days of Day 1 from patient recall; after randomization from the Patient Portal entries/diary entries or, if not available, from patient recall

 Visits 2 (Day 3), 3 (Day 10), and 4 (Week 3) can be performed virtually, via video link, if an ECG can be performed with direct transmission to site for review by investigator or designate and local laboratory assessments at Visit 4 can be arranged

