2.3.2 Additional efficacy endpoints of interest

Per section 4.1.3 of the study protocol (Amendment 2), additional efficacy endpoints are:

- Pain score using 11-point NRS from baseline (highest pain score within the past 7 days of Day 1) to Week 26 (highest pain score during the past 7 days of Week 26)
- - Percentage of patients with normalized CRP levels at 8 weeks (for patients with CRP ≥ 1.0 mg/dL at baseline)
- - Percentage of patients with pericarditis recurrence during the EP
- - Percentage of patients with normalized CRP levels at 26 weeks (for patients with CRP ≥ 1.0 mg/dL at baseline)
- - Time to CRP normalization for patients with CRP ≥ 1.0 mg/dL at baseline
- - CRP change from baseline at 26 weeks (%)

2.3.3 Additional efficacy endpoint of interest in Protocol amendment 2

Compared to protocol version 1, the endpoint 'Percentage of patients with pericarditis recurrence during the extension period (EP)' was added in protocol amendment 2.

Impact on statistical Analysis Plan:

Given that the data to ascertain this outcome will be available for all enrolled patients, there is no impact on the SAP / analysis for this additional endpoint added per protocol amendment 2.

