9.3 Precision

The precision of original measurements will be maintained in summaries. Where possible, means, medians and standard deviations will be presented with an increased level of precision; means and medians will be presented to one more decimal place than the raw data, and the standard deviations will be presented to two more decimal places than the raw data.

Percentages will be based on available data and denominators will exclude missing values. For frequency counts of categorical variables, categories where counts are zero will be displayed for the sake of completeness. For example, if none of the patients discontinue due to "lost to follow-up," this reason will be included in the table with a count 0. Categories with zero counts will not have zero percentages displayed.

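### The protocol gives two follow-up lengths for patients who stop study drug before Week 8, and the SAP treats extension-period recurrence as observed in all enrolled patients although non-entrants leave at Week 8

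*Protocol*

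**What the plan says.** **Patients who stop study drug.** Protocol 6.5.1 lists the situations in which treatment must stop for good. One of them is: "If the patient did not tolerate the starting dose of 5 mg/kg of body weight b.i.d". The same section then says of patients who discontinue that "unless they withdraw consent and are no longer willing to participate, they should be followed for the remainder of the trial". The Visit 2 text in Protocol 9.1 deals with the same intolerant patients and says that each of them "will continue in the study and follow all assessments until Visit 5 to be included in the safety analyses". Protocol 6.5.3, on withdrawal of consent, adds: "Reports of AEs and SAEs should be collected until completion of the study for all withdrawals", unless the patient objects.

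**Patients who do not enter the EP.** Under Protocol 6.2, entry at Week 8 is the default unless the investigator considers it contraindicated, and the EP consists of 18 further weeks on study drug while background therapy is weaned. The exposure table in SAP 8.4 also makes the extension a matter of patient agreement. Footnote 8 to the schedule in Protocol 17.2 reads: "For patients not able to participate in the EP, Visit 5 (Week 8) is the end of study visit". The Synopsis, Section 6.3 and the Visit 5 heading say the same. The general statements in Sections 15 and 4.2.2 refer to 26 weeks without an exception.

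**The analysis.** On the endpoint of recurrence during the EP, SAP 2.3.3 says: "Given that the data to ascertain this outcome will be available for all enrolled patients, there is no impact on the SAP". SAP 5 defines one set for efficacy, the Full Analysis Set (FAS) of everyone enrolled who started drug. SAP 8.5.2 derives recurrence from an adverse event with a given code between Weeks 8 and 26. Missing data are not imputed unless the SAP says otherwise (Protocol 11.4, SAP 9.2), and under SAP 9.3: "Percentages will be based on available data and denominators will exclude missing values".

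**The concern.** There are two separate problems.

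The first is a conflict in data collection. For a patient who stops drug early and keeps consent, one part of the protocol asks for 26 weeks of data and another for 8. Two sites could each follow the protocol and collect different data on the same kind of patient. These patients bear directly on the safety objective, whose stated period is 26 weeks.

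The second is in reporting. Anyone who leaves at Week 8 cannot be observed for recurrence in the EP, yet the SAP assumes that everyone can. If recurrence is tabulated over the FAS, a patient never observed after Week 8 has no coded event and may be counted as free of recurrence. For Week 26 CRP and pain the same patient has no value and drops out. The tables would not tell the reader which group each figure describes. Protocol 3.5 says the results are to inform the feasibility of a randomized withdrawal trial, and recurrence after weaning is a figure its designers would look to.

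**Working it through.** The plan has no figure to reproduce: Protocol 11.1 states that no formal sample size was calculated. The timeline itself is coherent. 8 + 18 = 26 weeks, and the SAP 8.4 day counts for amendment 2 are 2 + 7 + 47 = 56 days without the extension and 2 + 7 + 171 = 180 days with it. A patient who ends at Week 8 therefore has 18 of 26 weeks unobserved.

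**Step 1. Set the follow-up texts side by side.**

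| Patient | Text pointing to Week 26 | Text pointing to Week 8 |
|---|---|---|
| Does not tolerate the starting dose | 6.5.1, which names this case | 9.1, Visit 2 |
| Stops drug before Week 8 for another reason, consent kept | 6.5.1 | By inference: 6.2 makes the EP continued treatment, so 6.3, the Visit 5 heading and footnote 8 apply |
| Still on drug at Week 8, does not enter the EP | Only the general wording in 15 and 4.2.2 | Synopsis, 6.3, Visit 5 heading, footnote 8 |

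Row 1 is a direct contradiction. Row 2 is a conflict that no text resolves. In row 3 the operative sections agree on Week 8.

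**Step 2. Follow a patient with no data after Week 8 through the SAP.**

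- Recurrence: the derivation looks for a coded event. No record means no event, not a missing value, so the rule in SAP 9.3 need not remove the patient. With the FAS as the only efficacy set, the patient can stay in the denominator as recurrence-free.
- Week 26 CRP and pain: the value is missing, is not imputed, and leaves the summary.

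**Step 3. Size for recurrence.** The documents give neither the number of non-entrants k nor the number of recurrences x, so both are assumed, with 25 patients. Over entrants the figure is x/(25 − k), over all enrolled it is x/25, and if every non-entrant had relapsed it is (x + k)/25. The share of planned patient-weeks lost is 18k/(26 × 25) = 18k/650.

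| k | x | Over entrants | Over 25 enrolled | Upper bound | Patient-weeks lost |
|---|---|---|---|---|---|
| 1 | 5 | 5/24 = 20.8% | 20% | 6/25 = 24% | 2.8% |
| 3 | 4 | 4/22 = 18.2% | 16% | 7/25 = 28% | 8.3% |
| 5 | 4 | 4/20 = 20.0% | 16% | 9/25 = 36% | 13.8% |
| 8 | 3 | 3/17 = 17.6% | 12% | 11/25 = 44% | 22.2% |

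**Step 4. Size for Week 26 CRP normalization.** Assume 18 patients with baseline CRP ≥ 1.0 mg/dL, m of them without a Week 26 value, and 11 seen to be normalized. The available-data figure is 11/(18 − m), the lower bound is 11/18 = 61%, and the upper bound is (11 + m)/18.

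| m | Available data | Lower bound | Upper bound |
|---|---|---|---|
| 2 | 11/16 = 69% | 61% | 13/18 = 72% |
| 4 | 11/14 = 79% | 61% | 15/18 = 83% |
| 6 | 11/12 = 92% | 61% | 17/18 = 94% |

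Holding 11 fixed makes the available-data figure rise mechanically as m grows. The table shows how far the denominator matters; it does not predict the result.

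**The case against.** The best defence is that the protocol is mostly consistent and that the SAP knows about Week 8 completers.

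- *The general rule yields to the specific one.* Section 6.5.1 is general, and the end of the trial could mean Visit 5 for someone not in the EP. That reading is possible, but the text does not state it, and 6.5.1 itself names starting-dose intolerance. The conflict stands.
- *SAP 2.3.3 is a remark about the amendment.* It asks whether an endpoint added in amendment 2 can be derived for patients enrolled before it, and it covers that endpoint only. This is a fair account of its purpose. Taken as written, it still fails for anyone whose last visit is Week 8.
- *The SAP provides for Week 8 leavers elsewhere.* SAP 2.3.4 takes safety changes at the end of each patient's follow-up, either Week 8 or Week 26, and SAP 8.4 has a separate 8-week planned dose. So a reader who inferred that early leavers are lost from the safety results would be wrong. They contribute to those endpoints, and only the Week 26 rows of the by-visit tables are limited to patients still followed.
- *Disposition is already reported.* SAP 8.2 summarises why patients ended the study, and a CONSORT figure and a disposition listing are planned. This helps, but neither the table list nor the listing names EP non-entry with its reason.
- *Counting missing CRP as failure is severe.* A patient who left at Week 8 with a normal CRP would be counted as not normalized. That is why the figure may be shown only as a lower bound beside the planned one.

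**Conclusion.** The point holds in a limited form. Sections 6.5.1 and 9.1 contradict each other for patients who cannot tolerate the starting dose, and other patients who stop before Week 8 fall between 6.5.1 and the Week 8 exit rules. The statement in SAP 2.3.3 cannot be true for non-entrants, and the denominator for EP recurrence is not defined. Week 26 CRP and pain results describe those who remained.

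The documents do not support several stronger readings that a reader might draw:

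- That the inconsistency causes the selection at Week 26. The selection comes from the EP entry rule, on which the operative sections agree. Applying 6.5.1 to patients who stop drug would add Week 26 data.
- That the remaining patients are exactly those judged fit to wean. Patient agreement also decides entry, and Protocol 6.6 makes weaning subject to its own contraindication clause.
- That those missing are mainly drug stoppers. No figure is given.
- That the primary endpoint is compromised. It is measured at Week 8, at the point of EP entry, and the gate does not affect it.

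The size cannot be known from the documents. On the assumed counts the gap between the entrant and all-enrolled recurrence figures is about 1 to 6 percentage points, but the upper bound runs from 24% to 44%. If nearly everyone enters the EP, little changes. The point deserves correction because the remedy is cheap and alters what is reported.

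**What to change.** - **Protocol.** Reconcile 6.5.1, 6.3, the Visit 2 and Visit 5 text in 9.1, footnote 8 in 17.2 and Section 15 into one data-collection rule for patients who stop study drug. The sponsor should settle which length applies. Keeping such patients to Week 26 would add contacts, blood draws and clinical assessments that the schedule places in the EP, so it is not free.
- **SAP 2.3.3 and 8.5.2.** Remove the statement that the data exist for all enrolled patients. Define the EP entrants and report recurrence over them, with the number of non-entrants and their reasons in the same table.
- **SAP Week 26 outputs.** Label pain and CRP results as those of patients still followed, with the number contributing.
- **Week 26 CRP normalization.** Beside the available-data percentage, show the percentage over all treated patients with baseline CRP ≥ 1.0 mg/dL, counting a missing value as not normalized, and label it a lower bound.

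The SAP changes cost a little more table work and a second, less favourable CRP figure. None of them changes treatment or the primary analysis.

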#### Visit 5 (Week 8 ± 4 days) – final study visits for patients not continuing in the EP

The following evaluations will be performed at 8 weeks after start of study medication:

- Clinical assessment
- Vital signs, including HR, blood pressure and body weight
- Review/collection of daily diary NRS pain scores, if not submitted electronically to Patient Portal if the patient has completed the questionnaire on paper
- Collect highest NRS pain score within the past 7 days
- 12-lead ECG 5 hours post morning dose (time window 3.5 – 6 hours); QTc intervals on ECG to be reviewed by site investigator, or designate, who decides if patient can continue study medication
- C-SSRS
- Study drug accountability
- Recording of changes in concomitant medications
- Start weaning background therapy over the next 8 weeks for patients continuing in the EP
- AE and SAE recording
- Local laboratory assessments, including CRP, CBC, AST/ALT, alkaline phosphatase, bilirubin, creatinine/eGFR, INR

#### Visit 6 (Week 12 ± 4 days) – Virtual visit

The following evaluations will be performed virtually at 12 weeks after start of study medication:

- Review/collection of daily diary NRS pain scores, if not submitted electronically to Patient Portal
- Collect highest NRS pain score within the past 7 days
- Study drug accountability
- Recording of changes in concomitant medications
- AE and SAE recording

### Visit 7 (Week 16 ± 4 days)

The following evaluations will be performed at 16 weeks after start of study medication:

- Clinical assessment
- Vital signs, including HR and blood pressure
- Review/collection of daily diary NRS pain scores, if not submitted electronically to Patient Portal if the patient has completed the questionnaire on paper
- Collect highest NRS pain score within the past 7 days
- 12-lead ECG 5 hours post morning dose (time window 3.5 – 6 hours); QTc intervals on ECG to be reviewed by site investigator, or designate, who decides if patient can continue study medication
- Study drug accountability
- Recording of changes in concomitant medications
- AE and SAE recording
- Local laboratory assessments, including CRP, CBC, AST/ALT, alkaline phosphatase, bilirubin, creatinine/eGFR, INR

### Visit 8 (Week 20 ± 5 days) – Virtual visit

The following evaluations will be performed virtually at 20 weeks after start of study medication:

- Review/collection of daily diary NRS pain scores, if not submitted electronically to Patient Portal if the patient has completed the questionnaire on paper
- Collect highest NRS pain score within the past 7 days
- Study drug accountability
- Recording of changes in concomitant medications
- AE and SAE recording

### Visit 9 (Week 26 ± 5 days)

The following evaluations will be performed at 26 weeks after start of study medication:

- Clinical assessment
- Vital signs, including HR, blood pressure and body weight
- Review/collection of daily diary NRS pain scores, if not submitted electronically to Patient Portal if the patient has completed the questionnaire on paper
- Collect highest NRS pain score within the past 7 days
- 12-lead ECG 5 hours post morning dose (time window 3.5 – 6 hours)
- C-SSRS
- Study drug accountability
- Recording of changes in concomitant medications
- AE and SAE recording
- Local laboratory assessments, including CRP, CBC, AST/ALT, alkaline phosphatase, bilirubin, creatinine/eGFR, INR

***If a visit is missed and/or an ECG cannot be performed, the patient should stay on the current study drug dose until the next assessment.***

## **9.2 Clinical Procedures and Safety Evaluations**

### **9.2.1 Informed Consent**

Patients who comply with the eligibility criteria will be approached and informed of the possibility of study participation. The benefits and risks of participating in the study will be explained to the patient. The patient will be provided with an opportunity to read the detailed information about the study in an informed consent form (ICF) and ask any questions he/she may have. Prior to conducting any study-related procedures, the patient must provide consent to participate by signing the Institutional Review Board/Research Ethics Board (IRB/REB) approved ICF.

### **9.2.2 Demography**

This includes collection of age, sex and race.

### **9.2.3 Standard 12-lead Electrocardiogram (ECG)**

A 12-lead ECG will be performed at baseline, and at all in-person follow-up visits. Visits 2 (Day 3), 3 (Day 10) and 4 (Week 3) can only be virtual if an ECG can be performed and transmitted to the site for review.

The ECG after start of study medication will be recorded approximately 5 hours (time window 3.5 – 6 hours) post-morning dose ( $T_{max}$ ) to surveil for deleterious effects on ECG intervals (particularly the QTc interval) and rhythm. Continuation on study drug will be assessed by the investigator or designate dependent on interrogation of the ECG, most importantly the QT interval.

The QT interval can be obtained from the automated measurements of the ECG recorder unless the data quality is poor. In this case, the QT interval is measured from the beginning of the QRS complex to the end of the T wave and averaged over three cardiac cycles. The average QT interval should be corrected for heart rate variability using Bazett's formula ( $QT_c = QT / \sqrt{RR}$ ) or Fridericia's formula ( $QT_c = QT / RR^{1/3}$ ) to create the QTc interval. Each patient should have the QTc measured using the same method on all designated days in the study.

The presence of a bundle branch block (BBB) represents a particular challenge in properly measuring the QTc interval. Following international recommendations, QT interval should be measured in leads showing the longest QT interval, which is usually in right precordial leads. In presence of a BBB, these leads are strongest affected by conduction delay and therefore hamper adequate measurement. A new formula for evaluation of the QT interval in patients with left bundle branch block (LBBB) was introduced in 2014:

$$QT_{mean} = QT_{BBB} - 50\% QRS_{BBB} \text{ (Bogossian et al. 2014)}$$

This formula has proved to be a reliable tool in clinical practice for QTc interval evaluation in patients with LBBB, right bundle branch block (RBBB) or bifascicular block. (Bogossian et al. 2020; Erkacic et al. 2020)

Similarly, ventricular paced rhythm with an increased QRS duration can impact the QT interval. In patients with ventricular paced rhythm, 50ms should be subtracted from the Bazett's formula or Fridericia's formula.(Chakravarty et al. 2015)

If the QTc interval increases to 500 msec or more – or increases 60 msec or more from the baseline recording on any one measurement, this must be reported as an SAE and the study medication must be discontinued.

Other new clinically relevant ECG changes also need to be reported as an AE or SAE.

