### **5.3 Exclusion Criteria**

Patients meeting any of the following criteria will be excluded from the study:

1. Diagnosis of pericarditis that is secondary to specific prohibited etiologies, including tuberculosis (TB); neoplastic, purulent, or radiation etiologies; post-thoracic blunt trauma (e.g., motor vehicle accident); myocarditis
2. Estimated glomerular filtration rate (eGFR) <30 mL/min
3. Elevated alanine aminotransferase (ALT) or aspartate aminotransferase (AST) > 5 times the upper limit of normal (ULN) or ALT or AST >3x ULN plus bilirubin >2x ULN
4. Sepsis, defined as documented bacteremia at the time of screening or other documented active infection
5. Prior history of sustained ventricular arrhythmias
6. History of QT interval prolongation
7. QTc interval > 500 msec (please refer to Section 9.2.3 for bundle branch block, bifascicular block and paced rhythm correction)
8. Current participation in any research study involving investigational drugs or device
9. Inability or unwillingness to give informed consent
10. Ongoing drug or alcohol abuse
11. On any cannabinoid during the past month
12. Women who are pregnant or breastfeeding
13. Current diagnosis of cancer, with the exception of non-melanoma skin cancer
14. Any factor, which would make it unlikely that the patient can comply with the study procedures
15. Showing suicidal tendency as per the C-SSRS, administered at screening
16. On digoxin and/or type 1 or 3 antiarrhythmics
17. On immunosuppressive therapy with any of the following:
  - a. Rilonacept
  - b. Anakinra
  - c. Canakinumab
  - d. Methotrexate
  - e. Azathioprine
  - f. Cyclosporine
  - g. IVIG

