### **9.2.11    Management of AEs**

#### ***9.2.11.1   AE Reporting***

An AE is defined as any new untoward medical occurrence or worsening of a pre-existing medical condition in a patient or clinical investigation patient administered an investigational (medicinal) product and that does not necessarily have a causal relationship with this treatment. An AE can therefore be any unfavorable and unintended sign (including an abnormal laboratory finding, for example), symptom, or disease temporally associated with the use of investigational product, whether or not considered related to the investigational product.

AEs can be spontaneously reported or elicited during open-ended questioning, examination, or evaluation of a patient. (In order to prevent reporting bias, patients should not be questioned regarding the specific occurrence of one or more AEs.)

Any AE that results in any of the following outcomes will be considered an SAE:

1. Death

2. Life-threatening situation (patient was at risk of death at the time of the event. This does not refer to an event that might have caused death if it was of greater intensity.)
3. New in-patient hospitalization or prolongation of existing index hospitalization
4. Persistent or significant disability or incapacity
5. Congenital anomaly or birth defect
6. QTc interval increases to > 500 msec or >60 msec from baseline.
7. Important medical events that may not result in death, be life-threatening, or require hospitalization but may jeopardize the patient and may require medical or surgical intervention to prevent one of the above outcomes (based upon appropriate medical judgment), e.g., allergic bronchospasm requiring intensive treatment in an emergency room or at home, blood dyscrasias or convulsions that do not result in in-patient hospitalization, or the development of drug dependency or drug abuse. Potential Drug-Induced Liver Injury (DILI) is also considered an important medical event. (See Section 9.2.11.3 for the definition of potential DILI.)

All SAEs experienced by a patient after informed consent has been obtained must be reported to SOCAR Research (SOCAR) within 24 hours of the site's awareness of the event.

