8.3.9 Standard 12-lead Electrocardiogram (ECG)

Variable label:	Comment / category labels:
Ventricular rate	Tabulate as continuous variable in beats/min.
RR interval	Tabulate as continuous variable in milliseconds.
PR interval	Tabulate as continuous variable in milliseconds.
QRS interval	Tabulate as continuous variable in milliseconds.
QT interval	Tabulate as continuous variable in milliseconds.
QTc interval (Fridericia's formula)	Tabulate as continuous variable in milliseconds.

Variable label:	Comment / category labels:
Patients with abnormal ECG	Tabulate as categorical value = Yes. A Listing of ECG abnormalities considered clinically significant will be provided I

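### The protocol's QTc limits name no correction formula and differ at exactly 500 and 60 msec, and the SAP names Fridericia at baseline only, so limit events may not match the ECG table

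*Protocol*

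**What the plan says.** Protocol 9.2.3 states that "The average QT interval should be corrected for heart rate variability using Bazett's formula" and then offers Fridericia's formula as the alternative, with no basis for choosing. The paced-rhythm rule keeps both: "50ms should be subtracted from the Bazett's formula or Fridericia's formula". On the source of QT, "The QT interval can be obtained from the automated measurements of the ECG recorder unless the data quality is poor". The one consistency rule is "Each patient should have the QTc measured using the same method on all designated days in the study".

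Three limits depend on the result, and none names a formula:

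- Entry (Protocol 5.3): "QTc interval > 500 msec (please refer to Section 9.2.3 for bundle branch block, bifascicular block and paced rhythm correction"; such patients are excluded.
- Stopping and SAE reporting (Protocol 9.2.3): a QTc that reaches 500 msec or above, or a rise of at least 60 msec from baseline on any single measurement, is an SAE and ends study medication.
- SAE definition (Protocol 9.2.11.1): "QTc interval increases to > 500 msec or >60 msec from baseline".

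The readings are made locally (Protocol 9.1, Visit 2, repeated at later visits): "QTc intervals on ECG to be reviewed by site investigator, or designate, who decides if patient can continue study medication".

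SAP 8.3.9, the baseline ECG table, lists RR, QRS and QT and a single QTc variable, "QTc interval (Fridericia's formula)". Bazett does not appear in the SAP. SAP 8.6.5 plans absolute values and changes from baseline for ECG intervals and names no formula. No table counts patients who reach 500 or 60 msec.

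**The concern.** The same-method rule keeps each patient on one scale but does not put all patients on the same scale. Two patients with identical ECGs and different formulas could fall on opposite sides of a limit that decides entry, stopping or SAE status.

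ECG intervals are a named safety parameter (Protocol 4.2.2), and a QTc crossing is an SAE by definition. If a site works in Bazett and the SAP tabulates Fridericia, the SAE tables (SAP Tables 27 and 28) could hold a QTc event whose tabulated value never reached the limit. A tabulated value could also pass the limit with no event reported. With about 25 patients, one reclassified patient is 1/25, or 4 percentage points. No planned output would reveal the mismatch.

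**Working it through.** **Inputs.** The two formulas and the 500 and 60 msec limits come from Protocol 9.2.3. RR is in seconds, 60 divided by heart rate. The documents give no heart-rate distribution, so the rates below are assumptions. The plan has no figure of its own to reproduce here.

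**Step 1: relation between the formulas.** QTcB = QT / RR^(1/2) and QTcF = QT / RR^(1/3). Hence QTcB / QTcF = RR^(1/3 - 1/2) = RR^(-1/6). The ratio depends only on heart rate and equals 1 only at 60 bpm.

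**Step 2: the 500 msec limit.** The Fridericia value matching a Bazett value of 500 is 500 divided by the ratio.

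| Heart rate (bpm) | RR (s) | QTcB / QTcF | QTcF when QTcB = 500 |
|---|---|---|---|
| 50 | 1.200 | 0.970 | 515 |
| 60 | 1.000 | 1.000 | 500 |
| 70 | 0.857 | 1.026 | 487 |
| 80 | 0.750 | 1.049 | 477 |
| 90 | 0.667 | 1.070 | 467 |
| 100 | 0.600 | 1.089 | 459 |
| 120 | 0.500 | 1.122 | 445 |

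Example: a QT of 388 msec at 100 bpm gives QTcF = 388 / 0.8434 = 460 and QTcB = 388 / 0.7746 = 501. One ECG lies on both sides of 500.

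**Step 3: the 60 msec limit with no change in QTcF.** Hold QTcF at 420. QTcB is then 431 at 70 bpm, 441 at 80, 449 at 90 and 457 at 100. Moving between 70 bpm and 80, 90 or 100 bpm shifts QTcB by about 10, 18 or 26 msec, which is 16%, 31% or 44% of 60 msec on unrounded values. It is a rise if heart rate rises and a fall if it falls. Heart rate alone would need to go from 60 to about 134 bpm to produce 60 msec, since 60 x (1 + 60/420)^6 = 133.7.

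**Step 4: the 60 msec limit when QTcF does change.** One formula is used throughout for the patient.

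- Heart rate 100 to 70 bpm, QTcF 400 to 460 (+60): QTcB goes from 435.5 to 472.0 (+36). The limit in 9.2.3 is met on Fridericia and not on Bazett.
- Heart rate 70 to 100 bpm, QTcF 400 to 435 (+35): QTcB goes from 410.4 to 473.7 (+63). The limit is met on Bazett and not on Fridericia.

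Consistency within a patient therefore does not make the limits equivalent across patients.

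**Step 5: the limits side by side.**

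| Protocol section | Use | Value of exactly 500 msec | Rise of exactly 60 msec |
|---|---|---|---|
| 5.3 | Entry | Not excluded | Not applicable |
| 9.2.3 | Stop and report as SAE | Limit met | Limit met |
| 9.2.11.1, item 6 | SAE definition | Not met | Not met |

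Sections 9.2.3 and 9.2.11.1 give opposite SAE answers at both values, whatever the formula.

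**The case against.** Several points on the other side are fair.

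- A reader might infer that sites choose the formula. The protocol gives two formulas without saying who chooses. Local reading makes site choice plausible, but it is not stated, and a case report form or site manual may have fixed the formula.
- A reader might infer that the SAP analyses Fridericia throughout. That is explicit only at baseline. Follow-up use is a reasonable inference, because no other QTc is defined.
- The SAP lists QT, RR and Fridericia QTc for all patients with no exception for Bazett sites. Read plainly, it intends one scale; what is missing is a derivation statement, not a competing analysis.
- A reader might infer that heart rate falls as pericarditis resolves, so that Bazett hides a drug-related rise. No section says this and no heart-rate data are given. The shift runs in both directions. Above 60 bpm Bazett also reaches the absolute 500 msec limit sooner, so the effect is not simply one of masking.
- The study is single-arm, small and descriptive. SAEs are tabulated by MedDRA term, and no planned table sets them against ECG values.

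These points remove any claim about how often reclassification would occur or in which direction. They leave three facts standing: two formulas are permitted under limits that name neither, follow-up QTc has no stated formula, and two protocol sections conflict at the boundary values.

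**Conclusion.** The concern holds as an unstandardised safety rule and an incomplete SAP derivation. The same ECG can meet or miss a mandatory limit depending on which permitted formula is used. Over an assumed 50 to 100 bpm, a Bazett 500 msec corresponds to a Fridericia value between about 515 and 459 msec. Heart-rate differences of 10 to 30 bpm above 70 bpm move Bazett QTc by about 10 to 26 msec at a constant Fridericia value of 420. The boundary conflict between Protocol 9.2.3 and 9.2.11.1 needs no assumption.

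The number of patients affected cannot be estimated from the documents. The primary pain endpoint is untouched. The documents do not support saying that a QTc signal will be hidden, or that the SAE and ECG tables will disagree; they show only that they could, and that nothing planned would reveal it.

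**What to change.** **SAP 8.3.9 and 8.6.5.** State that the SAP's own QTc measure, Fridericia, is derived from recorded QT and RR for every ECG at baseline and follow-up, whatever formula was used at the site. Apply the bundle-branch and paced-rhythm adjustments of Protocol 9.2.3 where QRS and conduction or pacing status are recorded. Add a count of patients crossing the protocol's 500 and 60 msec limits on that scale. List every QTc-related SAE or stop with the formula and value that triggered it.

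**Protocol 5.3, 9.2.3 and 9.2.11.1, with SAP 8.3.9.** Reconcile these to one stated formula and one inequality for all sites. Which formula and which boundary should govern the clinical limits is for the sponsor and its clinical advisers; using Fridericia for the analysis does not settle it.

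**Cost.** A few SAP sentences, a little programming and a protocol clarification. QT, RR and QRS are already SAP variables. SAP 8.3.9 lists no conduction or pacing field, so the adjusted values may need a check of that status in the recorded data.
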